10.1. Sample Size Determination

Approximately 72 subjects will be enrolled so that approximately 60 healthy volunteers complete this study. This study is designed to test noninferiority (NI) of lasmiditan relative to placebo, with a diphenhydramine test versus placebo to confirm the sensitivity of the simulator to detect treatment effects. The following assumptions were made in the sample size computation: (a) SD of differences between lasmiditan and placebo within subject for SDLP is approximately 9.5 cm; (b) the true difference between lasmiditan doses and placebo is 0; and (c) the NI margin is proposed to be 4.4 cm, which is the effect seen with 0.05% of BAC. Under these assumptions, a sample of 60 subjects would provide >90% power to establish NI of either dose of lasmiditan compared to placebo in terms of the primary end point, SDLP. This sample size is more than adequate to detect diphenhydramine differences, which are anticipated to exceed the NI margin, from placebo.

Subjects who are randomized but who do not complete all 4 periods during the Treatment Phase may be replaced. Replacement subjects will enter the same treatment sequence as the original subjects to complete all 4 periods.

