Period 1, Day 1 subjects will be administered Dose 1 between approximately 0700 hours (7:00 AM) and 1000 hours (10:00 AM). On subsequent dosing days of Periods 2 to 4, doses will be administered at approximately the same time of day as doses in Period 1.

Approximately 8 hours following Dose 1, subjects will perform the CogScreen SDC test, KSS, and indicate their self-perceived safety to drive. Subjects will then perform the Country Vigilance-Divided Attention driving scenario on the CRCDS-MiniSim. Upon completion of the driving scenario, subjects will be administered a VAS to assess subjects' motivation and self-appraisal of their driving performance. Subjects repeat this testing procedure at approximately 12 hours and 24 hours after Dose 1 in all dosing periods.

While resident at the CRU, lights out will occur at approximately 2300 hours (11:00 PM) every night.

Subjects will remain a resident of the CRU from admission until discharge following the completion of study assessments. Blood draws for PK will be taken at pre- and post-dose according to the schedule of activities in all periods.

The total duration of subject participation will be approximately 5 weeks (range 3 to 7 weeks).

Number of Subjects:

Approximately 72 subjects will be enrolled so that 60 healthy volunteers complete the study. This will lead to 90% or more power for testing each of the hypotheses of primary interest regarding the driving assessment endpoints.

Statistical Analysis:**Safety:**

Safety analysis will be based on all subjects enrolled who receive at least 1 dose of study medication. The safety analysis will evaluate AEs and additional safety parameters. The number and percentage of subjects experiencing at least 1 AE will be summarized by body system, preferred term, and treatment. If appropriate, AEs will also be summarized by intensity and relationship to study drug. Serious adverse events, if any, will be tabulated.

Additional safety parameters will be assessed from summaries of physical examinations, 12-lead electrocardiograms and vital signs. Hematology, chemistry, and urinalysis laboratory test results will be categorized relative to the normal ranges. The changes from baseline for each of these parameters at postdose time points will be presented. Complete listings and summary tables for all safety information including AEs, laboratory safety data, vital signs, and physical examination will be included in the study report.

Pharmacokinetics:

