3.1. Study Rationale

Lasmiditan is a highly selective and potent agonist at the 5-hydroxytryptamine (5-HT)_{1F} receptor and is under development as a neurally acting treatment for migraine. The most frequently reported adverse events (AEs) identified in the lasmiditan clinical development program are central nervous system (CNS) in nature based on the mechanism of action of the drug. Due to treatment-related adverse effects of dizziness and fatigue observed in the Phase 2 clinical program, Study COL-MIG-106/H8H-MC-LAHG (106/LAHG) evaluating the impact of lasmiditan on driving performance was conducted in accordance with the United States Food and Drug Administration (FDA)'s Evaluating Drug Effects on the Ability to Operate a Motor Vehicle: Guidance for Industry (2017)

Study 106/LAHG was a randomized, subject-and investigator-blind, placebo-controlled, five-period, crossover study with the following treatments:

- Lasmiditan 50 mg
- Lasmiditan 100 mg
- Lasmiditan 200 mg
- Alprazolam 1 mg (positive control)
- Placebo

Subjects were randomized equally into 1 of 10 Latin square treatment sequences. The five periods were approximately 7 days in duration.

Period 1 → Washout 1 → Period 2 → Washout 2 → Period 3 → Washout 3 → Period 4 → Washout 4 → Period 5 → EOS
Day 1 Days 2-6 Day 7 Days 8-13 Day 14 Days 15-20 Day 21 Days 22-27 Day 28 Day 35

The simulated driving test was commenced 90 minutes after dosing (on Days 1, 7, 14, 21, and 28).

The effect of lasmiditan on simulated driving performance was primarily measured by the standard deviation of lateral position (SDLP) using the Cognitive Research Corporation Driving Simulator (CRCDS)-MiniSim. During testing, subjects were instructed to drive a 100-km highway segment with steady lane position and constant speed with a primary outcome measure of vehicle control, the SDLP (i.e. amount of "weaving" of the car in the lane).

Driving performance as assessed by SDLP was inferior for lasmiditan 50 mg, 100 mg, and 200 mg relative to placebo. This was further confirmed by symmetry analysis. A majority of

subjects exceeded the impairment threshold (4.4 cm, comparable to 0.05% blood alcohol count [BAC]) at even the lowest dose of lasmiditan. Sensitivity of the simulator and the model used in the research design were supported by significant findings on primary and secondary driving endpoints for alprazolam 1.0 mg.

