3.2. Background

Lasmiditan is being investigated for the acute treatment of migraine in adults with and without aura. Lasmiditan is a high-affinity, highly selective 5-HT (serotonin)_{1F} receptor agonist that is being developed as a novel therapy for the acute treatment of migraine. It has a chemical structure and pharmacologic profile that is distinct from the triptans, the current standard of care for the treatment of acute migraine. Lasmiditan does not contain the indole group observed in all triptans; instead it has a pyridinoyl-piperidine scaffold, which is unique to antimigraine medications. Lasmiditan is a low-molecular weight 5-HT_{1F} receptor agonist with a nonvascular, primarily neural mechanism of action. It has high affinity for the human 5-HT_{1F} receptor and >470-fold selectivity for the human 5-HT_{1F} receptor relative to the 5-HT_{1B} receptor. Across the completed Phase 1, 2, and 3 clinical studies, lasmiditan doses of 0.1 mg to 400 mg were evaluated in healthy subjects or patients with migraine. In two Phase 3, placebo-controlled studies in which patients treated 1 migraine attack with oral lasmiditan (50, 100, or 200 mg) or placebo, the most frequently reported lasmiditan treatment-emergent adverse events (TEAEs) were dizziness, paresthesia, somnolence, fatigue, lethargy, and nausea. A majority of these TEAEs were mild or moderate in severity. In healthy subjects, peak plasma concentrations of lasmiditan were observed approximately 1.5 hours to 2.5 hours after a single oral dose ranging from 25 mg to 400 mg, and the geometric mean terminal half-life was approximately 4 hours. Lasmiditan pharmacokinetics (PK) was approximately dose linear.

Following oral dosing with lasmiditan, up to 11 metabolites, including 3 major metabolites (M7, M8, and M18), were detected in human plasma and urine. These metabolites lacked significant pharmacological activity at the 5 HT_{1F} receptor and were generally considered to be pharmacologically inactive. The relative proportions of metabolites to intact lasmiditan

remained reasonably constant throughout the oral dose range studied and their PK was approximately linear. The half-life of the metabolites ranged from ~4.5 hours to 21 hours.

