5.4. Scientific Rationale for Study Design

Subjects will enter the CRU on Day -1. For the duration of the 4-period study, subjects will remain in the CRU. Each period will be of 3 days duration. It is anticipated that Study Periods 1, 2, 3, and 4 will commence on Study Days 1, 4, 7, and 10, respectively. For logistical reasons, the interval between periods may be extended by up to 2 days to accommodate site schedules. The minimum washout between periods is 3 days. Cognitive testing and driving simulation will be conducted approximately 8, 12, and 24 hours after Dose 1 on Day 1 of each study period. These driving assessment time points are expected to provide a wide range of responses including reversal of impairment.

The study design incorporates a positive control (diphenhydramine 50 mg) to confirm assay sensitivity. Per the FDA's Evaluating Drug Effects on the Ability to Operate a Motor Vehicle: Guidance for Industry (2017), sedating antihistamines are commonly used to understand the magnitude and duration of impairment. Diphenhydramine is a well-known sedating antihistamine available over the counter in the US and has been shown to have a significant

effect on driving performance (Kay et al. 1997, 2016). Diphenhydramine will be administered no more frequently than every 4 hours per package directions, coinciding with time points 2 hours prior to each driving assessment so that the maximum cognitive and sedative effect of the positive control coincide with the initiation of the driving simulation task.

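### The synopsis claims 90% or more power for every primary hypothesis, but the calculation supports that only for a single full-alpha test with a true difference of 0

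*Protocol*

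**What the plan says.** Protocol section 10.1, repeated in SAP section 7, lists three inputs: "SD of differences between lasmiditan and placebo within subject for SDLP is approximately 9.5 cm"; "the true difference between lasmiditan doses and placebo is 0"; and "the NI margin is proposed to be 4.4 cm, which is the effect seen with 0.05% of BAC". Neither dose nor time point is distinguished in the second input. The section then gives power above 90% for either dose with 60 completers, expressly conditional on those inputs.

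The synopsis (Number of Subjects) says that the enrolment target will give "90% or more power for testing each of the hypotheses of primary interest" on the driving endpoints. It repeats no condition. Protocol section 10.3.3.1 sets out the primary SDLP comparisons as two doses against placebo at three time points, which makes six noninferiority tests, two of them at 8 h.

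On what to expect at those times, section 5.4 says: "These driving assessment time points are expected to provide a wide range of responses including reversal of impairment". Section 3.1 reports that in the earlier driving study, at 90 minutes postdose, all three lasmiditan doses were inferior to placebo and a majority of "subjects exceeded the impairment threshold (4.4 cm, comparable to 0.05% blood alcohol count [BAC]) at even the lowest dose of lasmiditan". Section 3.2 gives a peak at roughly 1.5 to 2.5 h and near-linear pharmacokinetics, and says that "the geometric mean terminal half-life was approximately 4 hours".

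**The concern.** A study of duration of effect presupposes an effect that fades, and section 5.4 says as much. Planning all six tests on a zero difference sits badly with that, and the earliest drive is where zero is least secure. Section 10.1 at least shows the assumption. The synopsis does not, and a reader may take its figure as a property of each test.

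What is at stake is how a failed test is read. If the true difference is at or above 4.4 cm, failing to show noninferiority is the right answer. If it lies between 0 and 4.4 cm, the dose is noninferior by the protocol's own margin but the test may often fail. A reader who believes that each test has 90% power would tend to take such a failure as evidence of continuing impairment. Section 3.1 gives as the motive for the study that it is unclear when patients can resume driving, so the distinction matters.

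**Working it through.** **Inputs.** From protocol section 10.1: n = 60 completers (about 72 enrolled), SD of within-subject differences 9.5 cm, margin 4.4 cm, true difference d = 0. From section 10.3.3.1: noninferiority if the upper 95% confidence limit is below 4.4 cm, that is, two-sided 0.05. A paired comparison stands in for the mixed-model contrast.

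**Reproducing the plan's figure.**
- Standard error = 9.5/√60 = 1.226 cm.
- Normal approximation: power = Φ((4.4 − d)/1.226 − 1.960). At d = 0 this is Φ(3.588 − 1.960) = Φ(1.628) = 94.8%.
- Noncentral t on 59 df: 94.2%.
- Completers needed for 90% at d = 0: (9.5 × (1.960 + 1.282)/4.4)² = 49, rounded up.

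The statement of more than 90% is therefore reproduced.

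**Other true differences.** The documents give no SDLP difference at 8 h, so d is an assumed range. Each figure is for one test at full alpha, with no gating, n = 60.

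| True difference (cm) | Normal | Noncentral t |
|---|---|---|
| 0 | 94.8% | 94.2% |
| 0.5 | 88.9% | 87.9% |
| 1 | 79.2% | 77.8% |
| 2 | 49.9% | 48.6% |
| 3 | 20.7% | 20.1% |
| 4.4 | 2.5% | 2.5% |

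**Where 90% is lost.** Normal: d = 4.4 − (1.960 + 1.282) × 1.226 = 0.42 cm. Noncentral t: 0.36 cm, which is 0.36/4.4 = 8% of the margin. If all 72 enrolled subjects contributed, the noncentral t limit would be 0.72 cm.

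**How plausible is zero at 8 h?** Assume a simple exponential decline from the peak with a 4 h half-life, and dose-proportional concentrations. Concentration relative to the 50 mg peak is then (dose/50) × 2^(−(t − t_peak)/4), with t_peak from 1.5 to 2.5 h:
- 200 mg at 8 h: 4 × 0.324 to 4 × 0.386 = 1.30 to 1.54
- 100 mg at 8 h: 2 × 0.324 to 2 × 0.386 = 0.65 to 0.77
- 200 mg at 12 h: also 0.65 to 0.77
- 200 mg at 24 h: 0.08 to 0.10

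On these assumptions, 200 mg at 8 h is above the peak of a dose that was inferior at 90 minutes. The 100 mg dose at 8 h is below the peak of the lowest dose tested, so the earlier result says less about it.

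**Gating.** SAP section 9.4.3 sets w = 0.95, so after success at 100 mg, 24 h, the 200 mg, 24 h test first receives 5% of alpha: 0.05 × 0.05 = 0.0025 two-sided. At d = 0 and n = 60 the noncentral t gives about 66% power at that level. How much alpha reaches it later depends on Figure LAIF.3, which was not available in the text reviewed.

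**The case against.** The best defence is that nothing is miscalculated. Section 10.1 and SAP section 7 state the zero-difference assumption openly and make the power conditional on it. A zero difference is a common planning choice for noninferiority, and the synopsis only summarises. The testing order, from the latest time and lower dose towards earlier times and the higher dose, shows that the sponsor regarded 8 h as the hardest case. Differences with 95% confidence intervals are planned at every time point, so an inconclusive result will be visible as such. All of this stands, and it confines the point to the unconditional synopsis sentence and the missing sensitivity figures.

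It does not rescue the synopsis sentence. The synopsis does not define its hypotheses of primary interest, but section 10.3.3.1 attaches the primary endpoint to all six comparisons, so the natural reading includes 8 h.

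A reader might go further and infer that the pharmacokinetics and the earlier study contradict a zero difference at 8 h, or that 200 mg has almost no chance of passing there. The documents do not support that. They give no SDLP difference at 8 h and no mean difference even at 90 minutes. The half-life quoted is terminal, and a distribution phase would lower the 8 h concentration. Nothing in either document establishes that impairment follows plasma concentration; that relation is only to be explored.

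**Conclusion.** The point holds as a fault in how power is stated. The figure in section 10.1 and SAP section 7 is right for one test at full alpha with a true difference of 0. Carried without that condition to all six tests, it claims more than the calculation shows: a true difference of about 0.36 cm is enough to take an ungated test below 90%, and at 2 cm power is about a half.

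The power figures rest on the plan's own n, SD and margin. The doubt about zero at 8 h rests on section 5.4 and on the assumption that effect follows concentration; it is stronger for 200 mg than for 100 mg. For every test after the first, power under the sequential procedure is lower than the ungated figure. Type I error is not affected.

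**What to change.** 1. **Synopsis, Number of Subjects.** Remove the extension to every primary hypothesis. Suggested wording: *With 60 completers, an SD of within-subject differences of 9.5 cm and a true difference of 0, a single noninferiority test at two-sided 0.05 has more than 90% power.*
2. **Protocol section 10.1 and SAP section 7.** Add power at true differences of 1, 2 and 3 cm (78%, 49% and 20% with 60 completers), labelled as per-test and ungated. State that 90% is not claimed for the 8 h tests and that power under the sequential procedure is lower.
3. **Avoid one tempting replacement.** Do not say that 90% is planned for the 24 h tests. The 200 mg, 24 h test starts with 5% of alpha, where power is about 66% even at zero difference.

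The cost is a few sentences and a short table, plus a less favourable stated figure. Sample size, conduct and analysis do not change.

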10.2. Populations for Analyses

10.2.1. Study Participant Disposition

A detailed description of subject disposition will be provided at the end of the study.

10.2.2. Study Participant Characteristics

The subjects' year of birth, sex, weight, height, race, and other demographic characteristics will be recorded. Age and BMI will be calculated. Demographic and baseline characteristics will be summarized.

10.3. Statistical Analyses

Statistical analysis of this study will be the responsibility of Lilly or its designee. Complete details of the planned analyses will be contained in the statistical analysis plan.

Pharmacokinetic analyses will be conducted on data from all subjects who receive at least 1 dose of the investigational products and have evaluable PK.

Pharmacodynamic analyses will be conducted on data from all subjects who receive at least 1 dose of the investigational products and have evaluable PD.

Pharmacokinetic/pharmacodynamic analyses will be conducted on data from all subjects who receive at least 1 dose of the investigational products and have evaluable PK.

Safety analyses will be conducted for all enrolled subjects, whether or not they completed all protocol requirements.

Additional exploratory analyses of the data will be conducted as deemed appropriate. In general, categorical variables will be summarized by the count (N) and percentage of subjects (%). Continuous variables will be summarized by the number of non-missing observations (N), mean, SD, median, minimum, and maximum values.

10.3.1. Safety Analyses

10.3.1.1. Clinical Evaluation of Safety

All investigational product and protocol procedure AEs will be listed, and if the frequency of events allows, safety data will be summarized using descriptive methodology.

The incidence of symptoms for each treatment will be presented by severity and by association with investigational product as perceived by the investigator. Symptoms reported to occur prior to enrollment will be distinguished from those reported as new or increased in severity during the study. Each symptom will be classified by the most suitable term from the Medical Dictionary for Regulatory Activities.

The number of investigational product-related SAEs will be reported.

10.3.1.2. Statistical Evaluation of Safety

Safety parameters that will be assessed include safety laboratory parameters and vital signs. The parameters will be listed, and summarized using standard descriptive statistics. Additional analysis will be performed if warranted upon review of the data.

10.3.2. Pharmacokinetic Analyses

10.3.2.1. Pharmacokinetic Parameter Estimation

Plasma concentrations of lasmiditan, its metabolites, and diphenhydramine will be listed and summarized using descriptive statistics.

Pharmacokinetic parameter estimates for lasmiditan and its metabolites will be calculated using standard noncompartmental methods of analysis and summarized using descriptive statistics by dose level.

The primary parameters for analysis will be maximum observed drug concentration (C_{max}) and area under the concentration versus time curve (AUC). Other noncompartmental parameters, such as half-life, apparent clearance, and apparent volume of distribution may be reported.

10.3.3. Pharmacodynamic Analyses

The primary endpoint, SDLP, will be analyzed using a mixed model with fixed effects for sequence, period, and treatment, and a random effect for subject within sequence for each of the driving time points. Separate models will be used for each of the driving time points.

Secondary endpoints will be evaluated similarly; however, Lane Exceedance will be log transformed (more specifically, $\ln[x+1]$) prior to analyses. Pairwise comparisons for readiness to drive will be analyzed using McNemar test.

For the primary and secondary endpoints, pairwise comparisons (hypothesis tests) of differences in means, and 95% confidence intervals on differences will be provided at each time point for

1. Lasmiditan 100 mg versus placebo
2. Lasmiditan 200 mg versus placebo
3. Diphenhydramine 50 mg versus placebo

In addition, pairwise within-subject differences in SDLP greater than 4.4 cm in absolute value (equal to the previously found difference between placebo and 0.05% BAC for the CRCDS) will be compared using McNemar test. Furthermore, these pairwise, within-subject differences in SDLP will be tested for symmetry about zero using the maximally selected McNemar test.

10.3.3.1. Pharmacodynamic Statistical Inference

To address multiplicity of testing, 2 doses of lasmiditan versus placebo at 3 time points for the primary endpoint of SDLP, ascending doses of lasmiditan at descending time points will be interpreted in a sequential manner, starting with the 100-mg dose at 24 hours and proceeding to the 200-mg dose and earlier time points via a graphical multiple comparisons procedure ([Figure LAIF.3](#)). The value of w , the split of alpha after testing 100 mg at 24 hours, will be specified in the statistical analysis plan.

[figure not shown]

Figure LAIF.3. Pharmacodynamic statistical inference – graphical multiple comparisons procedure.

Doses of lasmiditan will be considered noninferior to placebo at a time point if the upper 95% confidence limit on the difference in SDLP between that dose and placebo is less than 4.4 cm. No adjustment to alpha levels will be made for the comparison of diphenhydramine either to placebo or to lasmiditan, or for secondary endpoints or analyses. Formal statistical tests (where performed) will be 2-sided with testing at the alpha=0.05 level of significance.

Appendix 1. Abbreviations and Definitions

Term	Definition
5-HT	5-hydroxytryptamine
AE	adverse event: Any untoward medical occurrence in a patient or clinical investigation subject administered a pharmaceutical product that does not necessarily have a causal relationship with this treatment. An AE can therefore be any unfavorable and unintended sign (including an abnormal laboratory finding), symptom, or disease temporally associated with the use of a medicinal (investigational) product, whether or not related to the medicinal (investigational) product.
ALP	alkaline phosphatase
ALT	alanine aminotransferase
AST	aspartate aminotransferase
AUC	area under the concentration versus time curve
BAC	blood alcohol count
blinding	A procedure in which 1 or more parties to the study are kept unaware of the treatment assignment(s). Unless otherwise specified, blinding will remain in effect until final database lock. A single-blind study is one in which the investigator and/or his staff are aware of the treatment but the subject is not, or vice versa, or when the sponsor is aware of the treatment but the investigator and/his staff and the subject are not. A double-blind study is one in which neither the subject nor any of the investigator or sponsor staff who are involved in the treatment or clinical evaluation of the subjects are aware of the treatment received.
BMI	body mass index
BP	blood pressure
CNS	central nervous system
complaint	A complaint is any written, electronic, or oral communication that alleges deficiencies related to the identity, quality, purity, durability, reliability, safety or effectiveness, or performance of a drug or drug delivery system.
compliance	Adherence to all the study-related requirements, good clinical practice (GCP) requirements, and the applicable regulatory requirements.
confirmation	A process used to confirm that laboratory test results meet the quality requirements defined by the laboratory generating the data and that Lilly is confident that results are accurate. Confirmation will either occur immediately after initial testing or will require that samples be held to be re-tested at some defined time point, depending on the steps required to obtain confirmed results.
CRCDS-MiniSim	Cognitive Research Corporation Driving Simulator-MiniSim
CRF	case report form

CRP	clinical research physician: Individual responsible for the medical conduct of the study. Responsibilities of the CRP may be performed by a physician, clinical research scientist, global safety physician, or other medical officer.
CRU	clinical research unit
CVDA	Country Vigilance-Divided Attention
DA	Divided attention
ECG	electrocardiogram
eCRF	electronic case report form
enroll	The act of assigning a subject to a treatment. Subjects who are enrolled in the study are those who have been assigned to a treatment.
enter	Subjects entered into a study are those who sign the informed consent form directly or through their legally acceptable representatives.
ERB	ethical review board
FDA	Food and Drug Administration
GCP	good clinical practice
HIV	human immunodeficiency virus
HRT	hormone replacement therapy
IB	Investigator's Brochure
ICF	informed consent form
ICH	International Council for Harmonisation
Investigational New Drug	An application to the FDA to allow testing of a new drug in humans.
informed consent	A process by which a subject voluntarily confirms his or her willingness to participate in a particular study, after having been informed of all aspects of the study that are relevant to the subject's decision to participate. Informed consent is documented by means of a written, signed, and dated informed consent form.
investigational product	A pharmaceutical form of an active ingredient or placebo being tested or used as a reference in a clinical study, including products already on the market when used or assembled (formulated or packaged) in a way different from the authorized form, or marketed products used for an unauthorized indication, or marketed products used to gain further information about the authorized form.

investigator	A person responsible for the conduct of the clinical study at a study site. If a study is conducted by a team of individuals at a study site, the investigator is the responsible leader of the team and may be called the principal investigator.
KSS	Karolinska Sleepiness Scale
LC-MS/MS	liquid chromatography tandem-mass spectrometry
legal representative	An individual or judicial or other body authorized under applicable law to consent, on behalf of a prospective subject, to the subject's participation in the clinical study.
NI	noninferiority
PK/PD	pharmacokinetic/pharmacodynamic
randomize	The process of assigning subjects to an experimental group on a random basis.
SAE	serious adverse event
screen	The act of determining if an individual meets minimum requirements to become part of a pool of potential candidates for participation in a clinical study.
SD	standard deviation
SDC	Symbol Digit Coding
SDLP	standard deviation of lateral position
SUSAR	suspected unexpected serious adverse reaction
TBL	total bilirubin level
TEAE	treatment-emergent adverse event: Any untoward medical occurrence that emerges during a defined treatment period, having been absent pretreatment, or worsens relative to the pretreatment state, and does not necessarily have to have a causal relationship with this treatment
ULN	upper limit of normal
VAS	Visual Analog Scale

